10.3 Statistical Methods

Unless otherwise specified, descriptive statistics for continuous variables include the number of patients with data (N), mean, standard deviation (SD), median, minimum, and maximum. The same number of decimal places as in the observed value are presented when reporting median, minimum, and maximum; one more decimal place than in the observed value is presented when reporting mean and quartiles; and two more decimal places than in the observed value is presented when reporting SD.

Categorical data are presented using frequency counts and percentages. All percentages are rounded to one decimal place, unless otherwise specified. Percentages equal to 100 are presented as 100% and no percentages are presented for zero frequencies. Where individual variable values are missing, summaries of categorical data are based on reduced denominators (i.e., the denominators include only patients with available data) and the number of missing values is presented.

The improvement of patient's experience in terms of comfort will be assessed using two-sided exact test of proportion to compare P_1 and P_0 . Further, the comfort levels of each device from all patients will be compared using t test. Linear mixed effect models will be utilized to compare the time duration of adjusting motion artifacts between two devices while accounting for inter-eyes correlations. The p values less than 0.05 will be considered as significant.

10 Source Documents and Access to Source Data/Documents

Source data is all information, original records of clinical findings, observations, or other activities in a clinical trial necessary for the reconstruction and evaluation of the trial. Source data are contained in source documents. Examples of these original documents, and data records include: hospital records, clinical and office charts, laboratory notes, memoranda, subjects' diaries or evaluation checklists, pharmacy dispensing records, recorded data from automated instruments, copies or transcriptions certified after verification as being accurate and complete, microfiches, photographic negatives, microfilm or magnetic media, x-rays, subject files, and records kept at the pharmacy, at the laboratories, and at medico-technical departments involved in the clinical trial. It is acceptable to use CRFs as source documents. If this is the case, it should be stated in this section what data will be collected on CRFs and what data will be collected from other sources.

The study case report form (CRF) is the primary data collection instrument for the study. All data requested on the CRF must be recorded. All missing data must be explained. If a space on the CRF is

Version: 3.0

left blank because the procedure was not done or the question was not asked, write "N/D". If the item is not applicable to the individual case, write "N/A". All entries should be printed legibly in black ink. If any entry error has been made, to correct such an error, draw a single straight line through the incorrect entry and enter the correct data above it. All such changes must be initialed and dated. DO NOT ERASE OR WHITE OUT ERRORS. For clarification of illegible or uncertain entries, print the clarification above the item, then initial and date it.

Access to study records will be limited to IRB-approved members of the study team. The investigator will permit study-related monitoring, audits, and inspections by the IRB/EC, government regulatory bodies, and University compliance and quality assurance groups of all study related documents (e.g. source documents, regulatory documents, data collection instruments, study data etc.). The investigator will ensure the capability for inspections of applicable study-related facilities (e.g. pharmacy, diagnostic laboratory, etc.).

Participation as an investigator in this study implies acceptance of potential inspection by government regulatory authorities and applicable University compliance and quality assurance offices.

11 Quality Assurance and Quality Control

QC procedures will be implemented beginning with the data entry system and data QC checks that will be run on the database will be generated. Any missing data or data anomalies will be communicated to the site(s) for clarification/resolution.

Following written SOPs, the monitors will verify that the clinical trial is conducted and data are generated, documented (recorded), and reported in compliance with the protocol, GCP, and the applicable regulatory requirements (e.g., Good Laboratory Practices (GLP), Good Manufacturing Practices (GMP)).

The investigational site will provide direct access to all trial related sites, source data/documents, and reports for the purpose of monitoring and auditing by the study staff and inspection by local and regulatory authorities.

12 Ethics/Protection of Human Subjects

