2.3 Rationale

This study primarily focuses on increasing the comfort for each patient's experience as well as reducing motion artifacts by improving the former, as well as stabilizing the patient's head, accomplished by adjusting the chin and forehead rest for each individual patient. The cohort will consist of a total of 90 subjects consisting of subjects that are both healthy and have an existing eye disease, as commonly observed in ophthalmology outpatient offices.

In order for certain limitations to not affect the validity of the results, various aspects of the trial will be randomized. This includes, but is not limited to, the order in which a patient will begin being imaged on either device C/N and which eye, OS/OD the Imager will scan first. This can help account for parameters including whether the time it takes to image the patient and/or level of comfort is affected as a result of their degree of alertness, energy level, how they are feeling on that particular day, etc.

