4.1 Description of Study Design

This is a randomized clinical trials study that includes two arms: experimental and control. The purpose of these arms is to compare the medical outcomes in terms of the subject's level of comfort as well as reducing the amount of motion artifacts. Subjects that are willing to participate will be required to participate in both arms.

Because the study design follows routine standard of care, there are no specific safety end points related to this project.

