4.2.2 Secondary Study Endpoints

A secondary objective includes evaluating various time durations while a patient is being imaged to determine whether the amount of motion artifacts are in fact being reduced by implementing the invention to existing devices. In one of the standard clinical OCT imaging devices, the Cirrus OCT, there is an eye tracking mode that can be activated whilst imaging a patient. This feature selects a specific location within the eye and will constantly adjust, i.e. track, for the fine fixation adjustments that occur when a patient's eye is moving very slightly. Therefore, in order to view whether there are a higher number of motion artifacts found in one image versus another, the Imager can time the duration it takes from the moment that they click "acquire", to when the progress bar is full. This is because the more time it takes for the system to fully acquire an image it directly correlates to how still the subject's eye is. Additionally, the data acquisition time can also be affected by whether the Imager is able to acquire a clear fundus photo, i.e. when there are no media opacities as well as if the Imager properly corrects for the refractive error.

5 Study Enrollment and Withdrawal

We aim to enroll 150 total subjects including healthy volunteers and subjects that have an existing eye disease including, but not limited to, glaucoma, AMD, DR, and CSCR. The site can actively enroll new subjects and these subjects will be are continuously followed in their institute. The total NYU cohort will include 150 healthy subjects as well as any eye related disease suspect subjects. There will be no enrollment restrictions based on gender, ethnic origin or HIV status and the study population will reflect the demographics of NYU Department of Ophthalmology. Subjects from clinical groups will participate in all applicable sub-studies of the protocol.

Subjects will be included in both groups, labelled as either Group 1 (Novel) or Group 2 (Conventional). Both groups will include subjects that are identified with glaucoma, age related macular degeneration, diabetic retinopathy, and central serous chorioretinopathy or any other eye related disease as well as healthy volunteers that are recruited from the clinic that undergo the clinical examination as part of their routine clinical management and healthy volunteers that are invited to the clinic to undergo the clinical examination for the purpose of the study.

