6.1.5 Administration

The order in which a subject will be imaged on either OCT imaging device C/N and whether the Imager will begin with either the OD/OS eye will be randomized. This will be done by providing the NYU Ophthalmology Clinic with a total of 90 envelopes that the Imager will choose from a mixed pile in which they will be evenly divided with a message to begin with device C/N and to begin with eye OD/OS.

The Standard Operating Procedure as to how to operate the novel device for imaging a subject can be seen below:

Version: 3.0

- 1. Sanitize chin and forehead rest
- 2. Seat subject by device
- 3. Move chinrest to either OD/OS
 - a. Slide chinrest to either right/left side
- 4. Size chinrest
 - a. Subject should place their chin in the rest and technician should either pull apart/push together the chin rest to either make it larger/smaller to fit the patient
- 5. Size mount of chinrest
 - a. Pull apart the mount easily to allow for the chinrest's length to be extended
- 6. Lock extension
 - a. Rotate knobs on both sides
- 7. Find correct/comfortable angular position of the chinrest
 - a. Push/move chinrest to position that it is comfortable i.e. not protruding into subject's neck and subject feels relaxed
- 8. Lock rotation
 - a. Tighten the bolt placed around the ball joint
- 9. Subject should rest forehead against the rest
- 10. Technician /imager should check if subject has to be adjusted closer to the device (based on the image from the device)
 - a. push/pull forehead rest by side of device so it will be adjusted along the grooved slot
- 11. Size forehead rest
 - a. tighten/loosen the strap on the side of the forehead rest to either make it smaller/larger for the patient (it will automatically lock into place)
- 12. Check if subject is comfortable, adjust if need be
- 13. Image subject according to scan protocol

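### The 0–5 comfort ratings come from a crossover with randomised device order, but Section 10.3 plans a t test that states no pairing and has no order term

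*Combined protocol and SAP*

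**What the plan says.** The design is within-subject. Section 4.1 states: "Subjects that are willing to participate will be required to participate in both arms". Section 6.1.5 randomises the device order and the first eye by envelopes, of which it says "they will be evenly divided with a message to begin with device C/N and to begin with eye OD/OS". Section 2.3 gives the reason for randomising, with reference to alertness, energy and how the subject feels that day: "This can help account for parameters including whether the time it takes to image the patient and/or level of comfort is affected".

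Section 4.2.1 builds the primary endpoint from two questions: which device was more comfortable, and a 0–5 comfort rating for each device. Section 10.3 tests the first with a two-sided exact test of one proportion. For the second it says "the comfort levels of each device from all patients will be compared using t test". Neither analysis has an order, period or sequence term. The time analysis that follows is a mixed model that names its correlation structure (between eyes), whereas nothing comparable is stated for comfort.

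Section 5 describes the devices as groups: "Subjects will be included in both groups, labelled as either Group 1 (Novel) or Group 2 (Conventional".

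Section 10.2 gives a power figure for the preference proportion only (80% at 65.7%, N=90). No power is given for the ratings.

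**The concern.** The protocol treats the first and second sessions as potentially different for comfort and randomises order for that reason. The rating analysis then leaves open whether it uses the pairing, and it does not use the order.

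Randomising order with balance protects the device contrast from bias. It does not remove the period effect from the error: half the subjects have their novel-minus-conventional difference shifted up and half have it shifted down. A paired t test that ignores order counts that spread as noise.

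The unstated pairing is a separate matter. An unspecified t test, beside language about two groups, leaves an analyst free to run either a paired or a two-sample test. When ratings from the same person are positively correlated, the two can differ widely. The choice should not be made after the data are seen, on a component of the primary endpoint.

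**Working it through.** **Inputs from the documents.** N=90, two-sided 0.05, null proportion 50% and alternative 65.7% (Section 10.2); enrolment target 150 (Sections 5 and 5.6); evenly divided orders (Section 6.1.5).

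**Assumed inputs, absent from the documents.** Rating SD 1; device difference δ = 0.3 SD; within-subject correlation ρ from 0 to 0.7; period difference π of 0, 0.25 or 0.5 SD.

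**The plan's own figure.** The two-sided exact test with N=90 rejects at 55 or more (or 35 or fewer), with attained level 0.0446. Power at 65.7% is 84.8%, not the stated 80%. A cutoff of 56, one step stricter than needed, gives 79.1%. At N=150 power is 97.0%. The stated figure is therefore low by about 5 points, which does not count against the preference test.

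**Ratings, N=90, ρ=0.5.** The within-subject difference has variance 2(1−ρ) = 1, so its true standard error is 1/√90 = 0.1054 and δ/SE = 0.3/0.1054 = 2.846.

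- Paired t, no period effect (critical value 1.987, 89 df): power 80.4%.
- Paired t, order ignored. With balanced orders the period difference adds π² to the estimated variance, so the critical value is in effect multiplied by √(1+π²).
  - π=0.25: 1.987 × 1.031 = 2.048; P(Z > 2.048 − 2.846) = 78.8%.
  - π=0.5: 1.987 × 1.118 = 2.221; P(Z > 2.221 − 2.846) = 73.4%.
  - Treating order as random instead (noncentral t with the inflated variance) gives 78.0% and 71.2%. The range is therefore 78–79% and 71–73%.
- Order fitted as a factor (88 df): 80.4% whatever the value of π.
- Two-sample t, if the text were read that way. The estimated standard error is √(2/90), which multiplies the critical value by 1/√(1−ρ) = 1.414: 1.973 × 1.414 = 2.791. True level 2·P(Z > 2.791) = 0.5%; power P(Z > 2.791 − 2.846) = 52%.

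| ρ (N=90, δ=0.3 SD) | Paired, order fitted | Paired, π=0.5 SD ignored (balanced) | Two-sample | Two-sample true level |
|---|---|---|---|---|
| 0 | 51% | 46% | 52% | 4.8% |
| 0.3 | 66% | 60% | 52% | 1.8% |
| 0.5 | 80% | 73% | 52% | 0.5% |
| 0.7 | 95% | 90% | 53% | 0.03% |

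At N=150 and ρ=0.5 the same quantities are 95%, 93%, 81% and 0.5%.

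**Preference, N=90, 45 subjects per order, marginal P1 held at 65.7%.** Here 70/30 means that, with no device difference, 70% would prefer the device in the favoured session. The within-order probabilities of preferring the novel device are then 83.4% and 48.0% (mean 65.7%); for 80/20 they are 91.4% and 40.0% (mean 65.7%). All figures are by exact enumeration.

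| Order effect | Pooled exact: power | Pooled exact: null rejection | Mainland-Gart, uncorrected: power | Mainland-Gart: null rejection |
|---|---|---|---|---|
| None | 84.8% | 4.5% | 84.9% | 4.5% |
| 70/30 | 86.6% | 2.8% | 91.2% | 5.3% |
| 80/20 | 89.0% | 1.2% | 96.1% | 5.4% |

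The pooled test grows conservative but loses no power against its stated alternative. It forgoes 91.2 − 86.6 = 4.6 points, or 96.1 − 89.0 = 7.1 points, at strong assumed order effects.

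**The case against.** The strongest reply is that this is a clarification and not a defect. Section 10.3 does not say unpaired, and ratings of each device by all patients fit a paired comparison naturally. The group sentence in Section 5 itself places every subject in both groups. No order effect is documented, and balanced randomisation keeps the contrast free of bias. All of this stands, and it limits how far the point goes. Four stronger readings are not supported.

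- **That the plan specifies a two-sample test.** The text is silent on pairing. The 52% figure shows what one reading would cost and does not describe the plan.
- **That order effects erode the preference test.** If the device effect is held at a fixed within-order log-odds of 0.65, pooled power falls to 73% (70/30) and 49% (80/20). But the marginal proportion then falls to 63.4% and 60.4%, and with no order effect at all those proportions would give about 71% and 49%. Section 10.2 defines its target as the marginal 65.7%, at which power does not fall.
- **That unequal orders will bias the result.** With a 54/36 split and a 70/30 order effect, the null proportion becomes (54×0.7 + 36×0.3)/90 = 54%, and the pooled test rejects 8.8% of the time. A split that uneven has probability of about 0.4% if 90 envelopes are drawn from an even 150. At 50/40 the level is 4.6%. Participation is a single visit, which leaves little room for differential withdrawal.
- **That Mainland-Gart should replace the exact test.** The pooled test holds its level under balanced orders. The uncorrected alternative slightly exceeds 5% under strong order effects at N=90. That is a trade-off and suits a sensitivity analysis.

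What the reply does not answer is why a component of the primary endpoint should be left to an unspecified t test when the design already supplies the pairing and the order.

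**Conclusion.** The point holds for the 0–5 ratings. The analysis should state that it is within-subject and should include the order that the protocol randomises.

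The size is conditional on inputs the documents do not give. At δ=0.3 SD, ρ=0.5 and N=90, ignoring order costs 1 to 2 points of power for a period effect of 0.25 SD and 7 to 9 points for 0.5 SD. It costs nothing if there is no period effect. The larger exposure is the unstated pairing: 52% against 80% if a two-sample test were run, with no loss at ρ=0.

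The preference test does not share the problem. It is already within-subject, remains valid with balanced orders, and at 65.7% has at least 84.8% power. A reader might infer that the comfort objective as a whole loses power or is biased. The documents do not support that.

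**What to change.** In Section 10.3:

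- Replace the unspecified t test with an analysis of each subject's novel-minus-conventional rating difference, with randomised device order as a factor (the standard two-period crossover analysis). A mixed model with a subject random effect and fixed effects for device and period is equivalent in purpose.
- Keep the pooled two-sided exact test as the preference analysis. Report preference by randomised order, with an order-stratified Mainland-Gart test as a sensitivity analysis only. That test needs a choice between the two devices, so state how a no-preference answer is handled; Section 10.2 currently defines the complement of P1 as no difference.
- State that the assigned order is captured in the dataset. Section 6.1.5 and the Schedule of Events describe selecting an envelope or imaging protocol, but no section says that the order is recorded as data.

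Two clerical changes would help: describe the two sequences (novel first, conventional first) in Section 5 in place of the group labels, and reconcile the envelope count (150 in the Schematic of Study Design, 90 in Section 6.1.5), since balance depends on it.

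The cost is one degree of freedom (89 to 88, with power unchanged at 80.4% in the example), a few sentences and a few lines of code. No new measurement is needed.

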12.1 Ethical Standard

The investigator will ensure that this study is conducted in full conformity with Regulations for the Protection of Human Subjects of Research codified in 45 CFR Part 46, 21 CFR Part 50, 21 CFR Part 56, and/or the ICH E6.

12.2 Institutional Review Board

The protocol, informed consent form(s), recruitment materials, and all participant materials will be submitted to the IRB for review and approval. Approval of both the protocol and the consent form must be obtained before any participant is enrolled. Any amendment to the protocol will require review and approval by the IRB before the changes are implemented to the study. All changes to the consent form will be IRB approved; a determination will be made regarding whether previously consented participants need to be re-consented.

Version: 3.0

12.3 Informed Consent Process

12.3.1 Consent and Other Informational Documents Provided to Participants

Consent forms describing in detail the study agent, study procedures, and risks are given to the participant and written documentation of informed consent is required prior to starting intervention/administering study product.

12.3.2 Consent Procedures and Documentation

Informed consent is a process that is initiated prior to the individual's agreeing to participate in the study and continues throughout the individual's study participation. Extensive discussion of risks and possible benefits of participation will be provided to the participants and their families. Consent forms will be IRB-approved and the participant will be asked to read and review the document. The investigator will explain the research study to the participant and answer any questions that may arise. All participants will receive a verbal explanation in terms suited to their comprehension of the purposes, procedures, and potential risks of the study and of their rights as research participants. Participants will have the opportunity to carefully review the written consent form and ask questions prior to signing. The participants should have the opportunity to discuss the study with their relatives or think about it prior to agreeing to participate. The participant will sign the informed consent document prior to any procedures being done specifically for the study. The participants may withdraw consent at any time throughout the course of the trial. A copy of the signed informed consent document will be given to the participants for their records. The rights and welfare of the participants will be protected by emphasizing to them that the quality of their medical care will not be adversely affected if they decline to participate in this study.

A copy of the signed informed consent document will be stored in the subject's research record. The consent process, including the name of the individual obtaining consent, will be thoroughly documented in the subject's research record. Any alteration to the standard consent process (e.g. use of a translator, , consent document presented orally, etc.) and the justification for such alteration will likewise be documented.

12.4 Participant and Data Confidentiality

Information about study subjects will be kept confidential and managed according to the requirements of the Health Insurance Portability and Accountability Act of 1996 (HIPAA). Those regulations require a signed subject authorization informing the subject of the following:

- What protected health information (PHI) will be collected from subjects in this study
- Who will have access to that information and why
- Who will use or disclose that information
- The rights of a research subject to revoke their authorization for use of their PHI.

In the event that a subject revokes authorization to collect or use PHI, the investigator, by regulation, retains the ability to use all information collected prior to the revocation of subject authorization. For subjects that have revoked authorization to collect or use PHI, attempts should be made to obtain permission to collect at least vital status (i.e. that the subject is alive) at the end of their scheduled study period.

Participant confidentiality is strictly held in trust by the participating investigators, their staff, and their agents. This confidentiality is extended to cover testing of biological samples and genetic tests in addition to the clinical information relating to participants. Therefore, the study protocol, documentation, data, and all other information generated will be held in strict confidence. No information concerning the study or the data will be released to any unauthorized third party without prior written approval of the study staff.

Version: 3.0

The study monitor, other authorized representatives of the study staff, representatives of the IRB or pharmaceutical company supplying study product may inspect all documents and records required to be maintained by the investigator, including but not limited to, medical records (office, clinic, or hospital) and pharmacy records for the participants in this study. The clinical study site will permit access to such records.

The study participant's contact information will be securely stored at each clinical site for internal use during the study. At the end of the study, all records will continue to be kept in a secure location for as long a period as dictated by local IRB and Institutional regulations.

Study participant research data, which is for purposes of statistical analysis and scientific reporting, will be transmitted to and stored at NYU Langone Medical Center. This will not include the participant's contact or identifying information. Rather, individual participants and their research data will be identified by a unique study identification number. The study data entry and study management systems used by clinical sites and by NYU Langone Medical Center research staff will be secured and password protected. At the end of the study, all study databases will be de-identified and archived at the NYU Langone Medical Center.

To further protect the privacy of study participants, a Certificate of Confidentiality will be obtained from the NIH. This certificate protects identifiable research information from forced disclosure. It allows the investigator and others who have access to research records to refuse to disclose identifying information on research participation in any civil, criminal, administrative, legislative, or other proceeding, whether at the federal, state, or local level. By protecting researchers and institutions from being compelled to disclose information that would identify research participants, Certificates of Confidentiality help achieve the research objectives and promote participation in studies by helping assure confidentiality and privacy to participants.

13 Data Handling and Record Keeping

